Appendix E: FACT-An (Version 4) (Continued)

[figure not shown]
Appendix E: FACT-An (Version 4) (Continued)

**APPENDIX F EQ-5D HEALTH QUESTIONNAIRES (EQ-5D-3L; ENGLISH
VERSION FOR THE US)**

Appendix F: EQ-5D Health Questionnaires (EQ-5D-3L; English Version for the US) (Continued)

[figure not shown]
APPENDIX G NEW YORK HEART ASSOCIATION CLASSIFICATION FOR CONGESTIVE HEART FAILURE

Functional Capacity
Class I. Subjects with cardiac disease but without resulting limitation of physical activity. Ordinary physical activity does not cause undue fatigue, palpitation, dyspnea, or anginal pain.
Class II. Subjects with cardiac disease resulting in slight limitation of physical activity. They are comfortable at rest. Ordinary physical activity results in fatigue, palpitation, dyspnea, or anginal pain.
Class III. Subjects with cardiac disease resulting in marked limitation of physical activity. They are comfortable at rest. Less than ordinary activity causes fatigue, palpitation, dyspnea, or anginal pain.
Class IV. Subjects with cardiac disease resulting in inability to carry on any physical activity without discomfort. Symptoms of heart failure or the anginal syndrome may be present even at rest. If any physical activity is undertaken, discomfort is increased.

Source: 1994 Revisions to Classification of Functional Capacity and Objective Assessment of Patients With Diseases of the Heart. American Heart Association website. Available at: <http://www.americanheart.org/presenter.jhtml?identifier=1712>. Accessed 02 Mar 2011.

APPENDIX H RECOMMENDATIONS FOR MANAGEMENT OF TREATMENT-INDUCED DIARRHEA

The following published guidelines ([Benson, 2004](#)) were modified in order to be consistent with the clinical study protocol.

APPENDIX I LIST OF ABBREVIATIONS AND DEFINITIONS OF TERMS

AE	Adverse event
AESI	Adverse event of special interest
ALT	Alanine transaminase (also SGPT)
AML	Acute myeloid leukemia
ANC	Absolute neutrophil count
AST	Aspartate transaminase (also SGOT)
BID	Twice a day
BUN	Blood urea nitrogen
CBC	Complete blood count
CCR	Conventional care regimen
CI	Confidence interval
CML	Chronic myeloid leukemia
CMML	Chronic myelomonocytic leukemia
CR	Complete remission
CRF	Case report form
CRO	Clinical research organization
CTCAE	Common Terminology Criteria for Adverse Events
DMC	Data Monitoring Committee
DNA	Deoxyribonucleic acid
EC	Ethics committee
ECG	Electrocardiogram
ECOG	Eastern Cooperative Oncology Group
EEA	European Economic Area
EP	Extension Phase
EPO	Erythropoietin
EQ-5D	EuroQol Group 5D
EMA	European Medicines Agency
ESA	Erythropoiesis stimulating agent
EU	European Union
FAB	French-American-British
FACT-An	Functional Assessment Cancer Therapy-Anemia
FCBP	Female of childbearing potential
FDA	Food and Drug Administration

Appendix I: List of Abbreviations and Definitions of Terms (Continued)

Fe/TIBC	Serum iron/serum total iron binding capacity
FISH	Florescent in situ hybridization
GCP	Good clinical practice
G-CSF	Granulocyte colony-stimulating factor
GM-CSF	Granulocyte macrophage colony-stimulating factor
Hgb	Hemoglobin
HBV	Hepatitis B virus
HCV	Hepatitis C virus
HI	Hematologic improvement
HI-E	Hematologic improvement-erythroid response
HI-N	Hematologic improvement-neutrophil response
HI-P	Hematologic improvement-platelet response
HIV	Human immunodeficiency virus
HLA	Human leukocyte antigen
HR	Hazard ratio
HRQoL	Health-related Quality of Life
IB	Investigator's Brochure
ICD	Informed Consent Document
ICH	International Conference on Harmonization
IMiD	Immunomodulating drugs
INR	International normalized ratio
INT-1	Intermediate-1
INT-2	Intermediate-2
IP	Investigational Product
IPSS	International Prognostic Scoring System
IRB	Institutional Review Board
IRT	Interactive Response Technology
ITP	Idiopathic thrombocytopenic purpura
ITT	Intent-to-Treat
IV	Intravenous
IVRS	Interactive Voice Response System
IWG	International Working Group
IWRS	Interactive Web Response System

Appendix I: List of Abbreviations and Definitions of Terms (Continued)

LDH	Lactic dehydrogenase
KM	Kaplan-Meier
MCH	Mean corpuscular hemoglobin
MCHC	Mean corpuscular hemoglobin concentration
mCR	Marrow complete response
MCV	Mean corpuscular volume
MDS	Myelodysplastic syndromes
MDS-U	Myelodysplastic syndrome -unclassified
MedDRA	Medical Dictionary for Regulatory Affairs
MH	Mantel-Haenszel
mITT	Modified intent-to-treat
MPD	Myeloidproliferative disease
NCI	National Cancer Institute
NYHA	New York Heart Association
OR	Odds ratio
OS	Overall survival
PIN	Personal Identification Number
PK	Pharmacokinetics
PR	Partial remission
pRBC	Packed red blood cells
PT	Prothrombin time
PTT	Partial thromboplastin time
QD	Once a day
RA	Refractory anemia
RAEB	Refractory anemia with excess blasts
RAEB-T	Refractory anemia with excess blasts in transformation
RARS	Refractory anemia with ringed sideroblasts
RCMD	Refractory cytopenia with multilineage dysplasia
RCUD	Refractory cytopenia with unilineage dysplasia
RDW	Red cell distribution width

Appendix I: List of Abbreviations and Definitions of Terms (Continued)

RBC	Red blood cell
ROW	Rest of world
RN	Refractory neutropenia
RNA	Ribonucleic acid
RT	Refractory thrombocytopenia
SAE	Serious adverse event
SC	Subcutaneous
SD	Stable disease
SDev	Standard deviation
SGOT	Serum glutamic oxaloacetic transaminase (also AST)
SGPT	Serum glutamic pyruvate transaminase (also ALT)
SMQ	Standardized MedDRA Query
SOP	Standard operating procedure
█	█
SUSAR	Suspected unexpected serious adverse reactions
TEAE	Treatment-emergent adverse event
TNM	Tumor nodes metastasis
TRALI	Transfusion-related lung injury
TSA	Thrombopoiesis-stimulating agent
ULN	Upper limit of normal
US	United States
WBC	White blood cell
WHO	World Health Organization

APPENDIX J EXTENSION PHASE

Once all 216 subjects enrolled have completed 12 months of double-blind treatment or have discontinued before reaching 12 months of double-blind treatment and Amendment 5 of the protocol is approved at the respective sites, and after study unblinding by Celgene, eligible subjects can enter the Extension Phase.

Subject Eligibility

At the Investigator's discretion and following confirmation of eligibility criteria below, subjects can enter the extension phase:

- Subjects who have signed the informed consent for the EP of the study;
- Subjects randomized to the oral azacitidine treatment arm and continuing in the Treatment Phase demonstrating clinical benefit as assessed by the Investigator are eligible to receive oral azacitidine in the EP;
- Subjects randomized into the placebo arm of the study will not receive oral azacitidine in the EP, but will be followed for survival in the EP;
- Subjects currently in the Follow-up Phase, after permanent study treatment discontinuation, will continue to be followed for survival in the EP;
- Subjects who do not meet any of the criteria for study discontinuation (see [Section 12](#)).

Treatment Assignment

Subjects will start the EP at the start of their next regularly scheduled dosing cycle for oral azacitidine and align Cycle 1 Day 1 with the Treatment Discontinuation visit, so they occur on the same day. The dose and schedule will follow the study treatment administration and schedule ([Section 8.2](#)).

Cycles should be repeated every 28 days. Subjects should be monitored locally for hematology and chemistry testing, pregnancy testing for FCBP and dose limiting toxicities before the dosing of the next cycle. Dosage delay or reduction as described below may be necessary.

Management of Toxicities and Dose Modifications

Subjects should be monitored for toxicity using the National Cancer Institute (NCI) Common Terminology Criteria for Adverse Events (CTCAE, Version 4.0), as a guide for the grading of severity. If a certain level of toxicity is observed and considered by the investigator to be at least possibly related to treatment, IP dosing may be interrupted, delayed or modified. In all cases, the reason for dose modification must be recorded in the subject's medical record. If the subject discontinues the protocol-prescribed therapy because of an AE, this event must be reported in accordance with the procedures outlined in [Section 12](#).

Oral azacitidine dose modifications due to nonhematological and hematological toxicities during oral azacitidine treatment should be managed as described in [Section 8.2.4](#) for dose modification guidelines due to toxicity.

Adverse Events

Adverse events (non-serious and serious) will continue to be collected in the EP AE CRF. Refer to [Section 11](#). Adverse Events for reporting requirements, responsibilities and procedures.

Concomitant Medications

All concomitant medications that are necessary for the subject's welfare may be given at the Investigator's discretion during the EP and recorded onto the CRF. However, treatment with any other investigational medication is not permitted. Refer to [Section 9](#) for prohibited concomitant medications/therapy for subjects on oral azacitidine.

Survival Follow-up

All subjects participating in the EP will be followed for survival, subsequent MDS therapies, progression to AML and secondary malignancy for 35 days \pm 7 days, including 28-day safety follow-up (refer to [Section 11.1](#): Monitoring, Recording, and Reporting of Adverse Events) following Treatment Discontinuation or until death, withdrawal of consent for further data collection, lost to follow-up, or study termination, whichever is earlier. The investigator must make every effort to obtain information regarding the subject's survival status before determining the subject is lost to follow-up.

Survival follow-up may be conducted via telephone contact with the subject, family, or the subject's treating physician or via record review (including public records, if admissible by law in the participating countries).

Monitoring of Subjects

The monitoring of subjects is as per the local standard of care, and at least:

- Complete blood count with WBC differential and platelet count as required, and at a minimum, prior to each dosing cycle
- For FCBP, pregnancy testing must be done prior to initiating a new cycle
- Bone marrow biopsy and aspirate as clinically indicated
- Additional tests or more frequent monitoring are at the Investigator's discretion based on the subject's clinical status.

Investigator's Responsibility

- Obtain subject's signature of the informed consent form to enter the EP phase
- Complete Extension Phase Case Report Form pages
- Document all adverse events (serious and non-serious) on the adverse event log page of the Extension Phase Case Report Form as required by the protocol ([Section 8.2.4](#))
- Report serious adverse events and other immediately reportable events, as required by the protocol (see [Section 11](#)). A completed SAE form must be faxed to Celgene Drug Safety, as detailed in the Serious Adverse Event Report Form Completion Guidelines, immediately (ie, within 24 hours of the Investigator's knowledge of the event)
- Report drug accountability to the sponsor

- Report to the sponsor and complete the case report form page for extension phase termination when the subject terminates treatment with oral azacitidine.
- The subject should stop treatment with oral azacitidine if any of the following occur:
 - Additional investigational treatment is started;
 - Subject is no longer receiving clinical benefit, as per Investigator’s discretion;
 - Subject withdraws consent;
 - A positive pregnancy test in a FCBP, at any time; or
 - At the specific request of the sponsor or its authorized representative.
- The Investigator must be available for periodic monitoring visits and allow the sponsor access to all medical records.
- The Investigator will maintain source documents on the subject for all case report form data points, which include the following:
 - Informed consent;
 - Adverse events;
 - Dosing information (date of administration, dose, number of tablets used, and lot number);
 - Concomitant-medications; and
 - Termination date and reason.

Safety evaluation for the EP will include monitoring for adverse events and recording of concomitant medications. Although physical examinations, vital sign measurements and laboratory assessments will be performed in the EP, these assessments will not be captured in the CRF. However, clinically significant findings from these assessments which meet the definition of an adverse event (see [Section 11](#)) will be reported as adverse events. Adverse events will be summarized as per [Section 10.7](#) on the subjects entering the EP. Exposure to oral azacitidine as well as concomitant medications taken during the EP will also be summarized.

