The decision to discontinue a subject, which will not be delayed or refused by the sponsor, remains the responsibility of the treating physician. However, prior to discontinuing a subject, the investigator may contact the Medical Monitor and forward appropriate supporting documents for review and discussion.

All subjects who have received at least one dose of IP should undergo Treatment Discontinuation procedures ([Section 6.13](#)) when treatment is discontinued.

The reason for discontinuation will be recorded in the case report form (CRF) and in the source document for all randomized subjects, regardless of whether they are dosed or not.

Follow-up Phase

All subjects discontinued from protocol-prescribed therapy for any reason will be followed for a period of 28 days following the last dose of IP or until the date of the last study visit, whichever period is longer, for the collection of AEs, concomitant medications, therapies and procedures, transfusions administered and healthcare resource utilization. Females of childbearing potential should avoid becoming pregnant for 3 months after the last dose of IP and male subjects should avoid fathering a child for 3 months after the last dose of IP.

All subjects discontinued from protocol-prescribed therapy for any reason will also be followed for survival, subsequent MDS therapies, progression to AML and second primary malignancy every month for the first year following Treatment Discontinuation and every three months thereafter until death, lost to follow-up, or withdrawal of consent for further data collection.

Extension Phase

At the Investigator's discretion and following confirmation of eligibility criteria below, subjects can enter the Extension Phase (EP):

Eligible Criteria:

- Subjects who have signed the informed consent for the EP of the study;
- Subjects randomized to the oral azacitidine treatment arm and continuing in the Treatment Phase demonstrating clinical benefit as assessed by the Investigator are eligible to receive oral azacitidine in the EP;
- Subjects randomized into the placebo arm of the study will not receive oral azacitidine in the EP, but will be followed for survival in the EP;
- Subjects currently in the Follow-up Phase, after permanent study treatment discontinuation, will continue to be followed for survival in the EP;
- Subjects who do not meet any of the criteria for study discontinuation (see [Section 12](#)).

Details for the EP are provided in [Appendix J](#).

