A sequential gate-keeping approach will be used to control the overall type I error rate in order to perform hypothesis testing on multiple endpoints. Two endpoints, the primary efficacy endpoint of RBC transfusion independence and the key secondary endpoint of OS, will be tested sequentially in the given, pre-specified order. The primary efficacy endpoint will be tested first at the two-sided 0.05 significance level. In order to preserve the overall alpha level at 0.05 across the RBC transfusion independence and OS endpoints, formal statistical inference for the OS analyses can only be made if superiority of azacitidine is demonstrated for the primary efficacy endpoint, RBC transfusion independence, at the two-sided 0.05 significance level.

The primary efficacy endpoint, RBC transfusion independence, will be analyzed and reported only once after all 100% of the information is available for RBC transfusion independence rates (ie, after all 216 subjects have completed 12 months (52 weeks [364 days]) of double-blind treatment or have been discontinued from treatment). An analysis of the OS endpoint will also be conducted at the time of the analysis of the primary efficacy endpoint. This analysis of the OS endpoint may be an interim analysis or it may be the final analysis, depending on the maturity of the survival data (e.g. the required 205 deaths have occurred) at the time of the final analysis for the RBC transfusion independence endpoint. An O'Brien-Fleming group sequential type boundary will be used to preserve the overall alpha level of 0.05 for the analysis of OS in the event that OS is analyzed twice.

The remaining secondary efficacy variables, with the exception of the proportion of subjects progressing to AML and time to AML progression, will be analyzed and reported once at the time of the analysis of RBC transfusion independence. Subjects will continue to be followed for progression to AML and survival until 205 deaths have been observed. Other than the pre-specified sequential testing of RBC transfusion independence and OS, no additional alpha adjustments for multiplicity will be made.

Study Closure

The study will conclude once all subjects have completed or discontinued from the extension phase.

Pathology Review

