6.6.2 Progression to AML and Second Primary Malignancies

Progression to AML and second primary malignancies will be monitored as events of interest and should be included as part of the assessment of AEs throughout the course of the study. Investigators are to report progression to AML and any second primary malignancy, regardless of causal relationship to IP (oral azacitidine or placebo), occurring at any time from signing of informed consent until death, lost to follow-up, or withdrawal of consent for further data collection. Events of progression to AML and second primary malignancy are to be reported as a serious adverse event (SAEs; considered to be an adverse event of special interest (AESI) even if no other seriousness criteria apply). This information must also be documented on the appropriate pages of the CRF and in the subject's source documents. Documentation on the diagnosis of progression to AML and/or the second primary malignancy (eg, any confirmatory histology or cytology results, X-rays, CT scans, etc.) must be provided at the time of reporting as an SAE. Refer to [Section 11.2](#) for evaluation of AEs.

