6.14 Follow-up

All subjects discontinued from protocol-prescribed therapy for any reason will be followed for a period of 28 days following the last dose of IP or until the date of the last study visit, whichever is later, for the collection of AEs, concomitant medications, therapies and procedures, transfusions administered and healthcare resource utilization. Females of childbearing potential should avoid becoming pregnant for 3 months after the last dose of IP and male subjects should avoid fathering a child for 3 months after the last dose of IP.

All subjects discontinued from protocol-prescribed therapy for any reason will also be followed for survival, subsequent MDS therapies, progression to AML and second primary malignancy every month for the first year following Treatment Discontinuation and every three months thereafter until death, lost to follow-up, or withdrawal of consent for further data collection. The investigator must make every effort to obtain information regarding the subject's survival status before determining the subject is lost to follow-up. Survival follow-up can be performed via the telephone.

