10.3 Sample Size and Power Considerations

The basis for the power and sample size determination will be a test of the equality of the overall survival curves between the azacitidine and placebo treatment groups using a stratified log-rank test. Assuming a median OS of 18 months in the placebo treated group (Garcia-Manero, 2008a), which takes into account possible cross-over outside of the protocol of placebo treated subjects to active treatment during the observation period, and a median OS of 25.7 months (43%

improvement) in the azacitidine treated group, 216 subjects (108 in each group) would have approximately 72% power to detect a constant hazard rate ratio of 0.70 using a two-sided log rank test with an overall significance level of 0.05. It is assumed that the OS distribution is exponential with a constant failure (hazard) rate and that accrual is uniform during the accrual period (56 months) with an overall drop-out rate of 5% from both treatment groups. Full information necessary for a log rank test to have 72% power will be achieved when approximately 205 deaths have occurred in both treatment groups, which is expected approximately 134 months after randomization of the first subject into the study.

An interim analysis of the OS endpoint may be performed and reported when all subjects have completed 12 months (52 weeks [364 days]) of double-blind treatment or have been discontinued from treatment (see [Section 10.8](#)).

While 56 days (8 weeks) is the standard duration a response must be maintained in order to meet the current IWG response criteria (IWG 2006 criteria; [Cheson, 2006](#); [Appendix D](#)), limited information is available on the target population for estimating the response rate for RBC transfusion independence maintained for ≥ 84 days (12 weeks).

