progression to AML and survival until 205 deaths have been observed. Other than the pre-specified sequential testing of RBC transfusion independence and OS, no additional alpha adjustments for multiplicity will be made.

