12 DISCONTINUATIONS

The following events are considered sufficient reasons for discontinuing a subject from the investigational product and/or from the study:

- Lack of Efficacy
- Progressive Disease ([Table 3](#))
- Adverse event(s)
- Withdrawal of consent
- Death
- Lost to follow up
- Protocol violation

Although lack of efficacy or progressive disease is considered a sufficient reason for discontinuing a subject from protocol-prescribed therapy, the investigator should continue to treat the subject until the investigator considers protocol-prescribed therapy to be no longer beneficial to the subject, or the change of disease state renders the subject unacceptable for further treatment in the judgment of the investigator. The decision to discontinue a subject, which will not be delayed or refused by the sponsor, remains the responsibility of the treating physician. However, prior to discontinuing a subject, the investigator may contact the Medical Monitor and forward appropriate supporting documents for review and discussion.

The reason for discontinuation will be recorded in the CRF and in the source document for all randomized subjects, regardless of whether they are dosed or not.

Subjects discontinued from the investigational product will not be replaced.

All subjects discontinued from protocol-prescribed therapy for any reason should undergo Treatment Discontinuation procedures ([Section 6.13](#)), and will be followed for a period of 28 days following the last dose of IP or until the date of the last study visit, whichever period is longer as described in [Section 6.14](#).

All subjects discontinued from protocol-prescribed therapy for any reason will also be followed for survival, subsequent MDS therapies, progression to AML and second primary malignancy as described in [Section 6.14](#).

Table 3: Definitions of Progressive Disease for Clinical Decision on Discontinuing Subjects from the Investigational Product and/or from the Study

Category	Progression/Relapse ^{†††} Criteria
Progression in Bone Marrow	
For subjects with:
 
Less than 5% blasts at baseline: > 50% increase in blasts to > 5% blasts
 
5%-10% blasts at baseline: ≥ 50% increase to > 10% blasts
 
Note: A 2nd bone marrow sample should be collected within 4 weeks to confirm progression before discontinuing subjects from treatment.

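### Amendment 6.0 shortened Extension Phase survival follow-up to 35 ± 7 days after treatment ends, but the overall-survival target of 205 deaths and 72% power was left unchanged

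*Protocol*

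**What the plan says.** Appendix J (Survival Follow-up) sets the rule for the Extension Phase (EP): "All subjects participating in the EP will be followed for survival, subsequent MDS therapies, progression to AML and secondary malignancy for 35 days", ± 7 days, after Treatment Discontinuation, or less if death, withdrawal of consent, loss to follow-up or study termination comes first. The rationale for Amendment 6.0 says openly that this replaces follow-up until death, to reduce burden after the primary study report was final.

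The OS design passages keep the longer follow-up:

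- Protocol Summary (Analysis and Reporting): "Subjects will continue to be followed for progression to AML and survival until 205 deaths have been observed".
- Section 10.6 keeps the same rule: "progression to AML and survival until 205 deaths have been observed".
- Section 10.3: "Full information necessary for a log rank test to have 72% power will be achieved when approximately 205 deaths have occurred", expected about 134 months after the first randomization.

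The timing of the final OS analysis is stated in two ways. Section 10.6 ties it to the required 205 deaths. Section 10.6.2.1 places it at study closure, which Section 4.1.5 defines as the point when all subjects have completed or left the EP.

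On who is covered, Appendix J (Subject Eligibility) says that placebo subjects, and subjects already off treatment, will be followed for survival in the EP. EP entry requires consent. Section 6.14 keeps the general follow-up rule: "every three months thereafter until death, lost to follow-up, or withdrawal of consent for further data collection".

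**The concern.** OS is the only secondary endpoint under alpha control. Its event count and power assume follow-up that the current protocol no longer provides for EP subjects. Someone reading Sections 10.3 and 10.6 would expect a final analysis on 205 deaths with 72% power, and would not learn that the event count must fall short if most survivors are in the EP. The two triggers leave open whether final OS waits for a death count or for closure. For placebo and off-treatment subjects, a window counted from Treatment Discontinuation may have closed before the amendment existed, although the same appendix says they will be followed for survival. What is at stake is information and clarity about the final OS analysis.

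**Working it through.** **Inputs** (Section 10.3): exponential survival; medians 18 and 25.7 months; 108 per arm; uniform accrual over 56 months; overall drop-out 5%; hazard ratio 0.70; two-sided alpha 0.05.

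**1. Reproduce the stated power.** Schoenfeld: power = Φ(½√D × |ln 0.70| − 1.960). For D = 205: ½ × 14.318 × 0.3567 = 2.553; 2.553 − 1.960 = 0.593; Φ = 72.4%. The stated 72% is right for 205 deaths.

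**2. What 205 deaths requires.** 216 − 205 = 11 subjects may lack an observed death. The plan's 5% drop-out alone uses 216 × 0.05 = 10.8.

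**3. Expected deaths by calendar month T.** With λ = ln 2 / median (0.03851 placebo, 0.02697 azacitidine) and no drop-out, the mean fraction alive is [e^(−λ(T−56)) − e^(−λT)] / (56λ). At T = 80:

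- Placebo: (0.3968 − 0.0459) / 2.1565 = 0.163, so 17.6 alive and 90.4 dead.
- Azacitidine: (0.5235 − 0.1156) / 1.5104 = 0.270, so 29.2 alive and 78.8 dead.
- Total: 169.3 deaths before rounding.

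For 5% drop-out, a competing hazard γ = λ × 0.05/0.95 replaces λ by λ + γ in the fraction still alive and followed. Deaths are then 108 × 0.95 × (1 − that fraction) per arm.

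**4. Why months 80 and 92.** The protocol does not date the truncation. Planned primary analysis: 56 + 12 = month 68. From the data cut-off (25-Jan-2019) to the date by which the report was final (04-Feb-2020) is 375 days, or 12.3 months, which gives about month 80. Month 92 allows one more year. Both place real dates on the planned timeline and are assumptions.

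**5. Results** (5% drop-out to none):

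| Scenario | Deaths | Power |
|---|---|---|
| Stated in Section 10.3 | 205 | 72% |
| Before the amendment, month 134 | 197.9–207.0 | 70.8–72.8% |
| All follow-up ends month 80 | 163.9–169.3 | 62.7–64.1% |
| All follow-up ends month 92 | 177.3–183.8 | 66.1–67.7% |
| Half of survivors end at month 80, rest to 134 | 180.9–188.1 | 66.9–68.7% |
| Half of survivors end at month 92, rest to 134 | 187.6–195.4 | 68.5–70.3% |

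The half-and-half rows average the truncated and month-134 counts; for example, (169.3 + 207.0)/2 is about 188.1. None of the truncated scenarios reaches 205. At month 80, about 44 to 47 subjects would still be alive and in follow-up, against the 11 that the target can spare.

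**6. Effect on Section 10.8.** The 68% interim fraction is 0.68 × 205 = 139 deaths. Against 164 to 169 final deaths the same 139 would be about 82% to 85% of the information. Section 10.8 already lets the levels follow actual events, so only the projected fraction and the final level that goes with it are out of date.

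**The case against.** The strongest reply is that the shortening was a disclosed choice and that the protocol says where the EP rule sits. Both parts stand. A reader might infer that the plan never says follow-up differs by EP status. It does: the Amendment 6.0 rationale confines the change to EP patients, and Sections 4.1.4 and 6.15 and Table 1 footnote hh send EP subjects to Appendix J. Sections 4.1.3, 6.14 and 12 therefore read as a general rule beside a specific one. They lack a cross-reference, but they do not conflict with Appendix J in the way Section 10.6 does.

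The reporting rules for AML and second malignancy in Sections 6.6.2, 10.7 and 11.5 are weaker still as contradictions. Their wording ties them to the course or duration of the study, so they can be read as reporting duties while a subject is in it.

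Nor can it be said that final OS cannot be run. Censoring at last contact is defined in Section 10.6.2.1, closure is defined, and the SAP Introduction defers final OS to a separate analysis. The SAP was written to Amendment 5, so its own 205-death text is not an Amendment 6.0 error.

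A reader might also infer bias, because only azacitidine subjects can remain on drug and hence under longer follow-up. The documents do not give the number still treated or the data cut for final OS, so neither the direction nor the size of a bias can be shown.

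Finally, the true loss depends on facts not given, and it may be only a few points. That also stands. None of this updates the 205-death rule or the 72%.

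**Conclusion.** The point holds. Appendix J ends survival and AML follow-up of EP subjects shortly after treatment stops, while the Protocol Summary and Sections 10.3 and 10.6 still describe a design that follows nearly everyone to death. The 72% is not an arithmetic error; the follow-up behind it was removed. If most survivors are in the EP and follow-up ends at about month 80 to 92, about 164 to 184 deaths and 63% to 68% power are expected. Power rises to about 70% if half of survivors stay outside the EP or remain under follow-up. The comparator is about 71% to 72% before the amendment. It would be wrong to quote any one of these as the trial's actual power: truncation month, EP uptake, numbers still on azacitidine and observed deaths are all absent from the documents. Two smaller gaps are confirmed by the text alone: the two triggers for final OS, and the undefined start of the window for placebo and off-treatment subjects.

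**What to change.** - In the Protocol Summary and Sections 10.3, 10.6 and 10.6.2.1, remove the 205-death and month-134 target or mark it as superseded by Amendment 6.0.
- Name one trigger for final OS that is not chosen from the data, for example study closure as Section 4.1.5 defines it.
- Analyse the deaths actually observed, with the Lan-DeMets final level recomputed from the actual information, and restate the lower expected power with its assumptions.
- Carry the same text into the separate final-OS plan.
- In Appendix J, reconcile the eligibility list with the follow-up paragraph by stating the date from which the 35-day window runs for subjects already off treatment.
- In Sections 4.1.3, 6.14 and 12, add a cross-reference to Appendix J for EP subjects.

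Two heavier remedies are not needed. Cutting both arms at the amendment date would discard later valid deaths, and restoring longer telephone follow-up would reverse a deliberate, disclosed choice.

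The cost is wording, a short final-OS plan, a less favourable stated power, and disclosure that the trigger was set after unblinding.
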